**Table 1: Table of Events (Continued)**

Phases	Screening Phase	Double-blind, Placebo-Controlled Treatment Phase (12 weeks)								Active Treatment Phase (52 weeks)					Post-treatment Observational FU Visit (4 weeks after last dose of IP) a)	Early Termination (ET) b)
		2 Randomization	3	4	5	6	7	8	9	10	11	12	13	14		
Visit Number	1	2	3	4	5	6	7	8	9	10	11	12	13	14	15	
Week	-6 to 0	0	1	2	4	6	8	10	12	16	28	40	52	64	68	
Day	-42 to 0	1	8 ±1	15 ±1	29 ±3	43 ±3	57 ±3	71 ±3	85 ±3	113 ±7	197 ±7	281 ±7	365 ±7	449 ±7	476 ±7	
Chest Radiograph n	X	-	-	-	-	-	-	-	-	-	-	-	-	-	-	-
12-lead ECG o	X	-	-	-	-	-	-	-	-	-	-	-	-	-	-	-
Efficacy Assessments																
Number of Oral Ulcers	X	X	X	X	X	X	X	X	X	X	X	X	X	X	X	X
Number of Genital Ulcers	X	X	X	X	X	X	X	X	X	X	X	X	X	X	X	X
Pain VAS for Oral Ulcers	X	X	X	X	X	X	X	X	X	X	X	X	X	X	X	X
Pain VAS for Genital Ulcers	X	X	X	X	X	X	X	X	X	X	X	X	X	X	X	X
BD Current Activity Form	-	X	-	-	-	-	-	-	X	-	-	-	-	X	X	X
BD Quality of Life Measure	-	X	-	-	-	-	-	-	X	-	-	-	-	X	X	X
BSAS	-	X	-	-	-	-	-	-	X	-	-	-	-	X	X	X
Physician's Global Assessment of Skin Lesionsp																
Physician's Global Assessment of Skin Lesions p	-	X	X	X	X	-	X	-	X	X	X	X	X	X	X	X
Assessment of BD-related Inflammatory Eye Diseaser																
Assessment of BD-related Inflammatory Eye Disease r	X	-	-	-	-	-	-	-	X	-	-	-	-	X	-	X

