#### Disease Specific Parameters:

3. Diagnosed with Behçet's disease meeting the International Study Group (ISG) criteria ([Appendix K](#)).
4. Oral ulcers that occurred at least 3 times in the previous 12-month period, including oral ulcers at the Screening Visit.
5. Subjects must have at least 2 oral ulcers at Visit 1 (Screening Visit), and:
  - a) at least 2 oral ulcers at Visit 2 (day of randomization), when Visit 2 occurs at least 14 days after Visit 1,
  - OR**
  - b) at least 3 oral ulcers at Visit 2 (day of randomization), when Visit 2 occurs at any time between 1 day and 42 days after Visit 1.
6. Have prior treatment with at least 1 non-biologic BD therapy, such as, but not limited to, topical corticosteroids, or systemic treatment.
7. Candidate for systemic therapy, for the treatment of oral ulcers.
  - a. A candidate for systemic therapy is a subject judged by the study Investigator as someone whose mucocutaneous ulcers are considered inappropriate for topical therapy based on the severity of disease and extent of the affected area, or whose oral ulcers cannot be adequately controlled by topical therapy.
8. Laboratory Measures: Must meet the following laboratory measures:
  - Hemoglobin  $> 9$  g/dL

- White blood cell (WBC) count  $\geq 3000$  / $\mu\text{L}$  ( $\geq 3.0 \times 10^9/\text{L}$ ) and  $\leq 14,000/\mu\text{L}$  ( $\leq 14 \times 10^9/\text{L}$ )
- Platelet count  $\geq 100,000$  / $\mu\text{L}$  ( $\geq 100 \times 10^9/\text{L}$ )
- Serum creatinine  $\leq 1.5$  mg/dL ( $\leq 132.6$   $\mu\text{mol}/\text{L}$ )
- Total bilirubin  $\leq 2.0$  mg/dL
- Aspartate transaminase (AST [serum glutamic oxaloacetic transaminase, SGOT]) and alanine transaminase (ALT [serum glutamate pyruvic transaminase, SGPT])  $< 1.5 \times \text{ULN}$ . Subjects who fail screening due to  $\geq 1.5 \times \text{ULN}$  AST/SGOT and/or ALT/SGPT will be allowed to repeat AST/SGOT and/or ALT/SGPT tests within the Screening Phase. Repeat test results should be  $\leq \text{ULN}$  (within reference range) to be eligible.

Laboratory tests will be allowed to be repeated 1 time if, in the Investigator's clinical judgment, there is a reasonable possibility of the repeat tests not meeting the exclusion values, and with concurrence from the Medical Monitor.

9. Contraception Requirements:

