4.4. Sample Size Determination

The sample size estimation is based on the consideration from the results of the Phase 2 study CC-10004-BCT-001. A 2-sided t-test at a 0.05 significance level will have 90% power to detect a treatment difference of 66 in the AUC of oral ulcer counts from Day 1 through Week 12 (AUC₈₅ of placebo – drug = 66), the primary efficacy endpoint, when the sample size in each group is 102, assuming a common standard deviation of 144.

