5.3. Baseline Definitions

For all efficacy analyses and the data tabulation of baseline disease characteristics, baseline is defined as the last value measured on or before the day of the first dose of IP. For the summaries of laboratory parameters, vital signs, and weight, baseline is defined as the last value measured on or before the day of the first dose of IP in the summaries for the placebo-controlled period, and defined as the last value measured on or before the start day (defined in Section 5.2) of the apremilast-exposure period in the summaries for the apremilast-exposure period.

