10.2.2. Analysis of Primary Efficacy Endpoint

The primary efficacy endpoint is the AUC for the number of oral ulcers from Day 1 through Week 12/Day 85 (AUC₈₅). The AUC₈₅ will be compared between the placebo and APR 30 BID groups using a two-tailed parametric ANCOVA test at the 0.05 level. The model will include AUC₈₅ as the response variable; treatment, sex and region as factors; and the number of oral ulcers at baseline as a covariate. Within-group least-squares (LS) means, the associated standard errors (SE), and treatment differences in LS means, the associated SE, and associated 2-sided 95% CIs and 2-sided p-values will be derived from the model. The primary efficacy analysis will be performed using the ITT and PP population.

To derive AUC₈₅, the multiple imputation (MI) method will be used to impute missing oral ulcer counts on study visits from Day 1 through Week 12 with 3 steps:

- Check missing data patterns;
- If there are non-monotone patterns, then use the Markov Chain Monte Carlo (MCMC) with a single chain method to impute sufficient missing oral ulcer counts by treatment to make 25 data sets having monotone patterns only. The seed will be set to 37851. When the imputed oral ulcer count post-baseline is negative, the value of 0 will be assigned.
- For the monotone datasets, use the predictive mean matching method with treatment, sex, region, and oral ulcer counts from previous visits as covariate to impute the remaining missing oral ulcer counts to make datasets complete. The MONOTONE REGPMM statement will be used with a seed of 37951.

In this MI approach, instead of filling in a single value for each missing value, SAS® procedure PROC MI performs MI by replacing each missing value with a set of plausible values. The missing data will be filled in multiple times to generate multiple complete data sets. A supportive analysis based on PP population will be performed using MI approach with the same seed number on PP population.

Missing data patterns will be provided in a separate table. The results obtained from parametric ANCOVA models (one for each imputation) will then be combined to derive valid statistical inference through the SAS® procedure PROC MIANALYZE. The complete-data degrees of freedom for parameter estimate specified in the PROC MIANALYZE option will be pulled from degree of freedom from parametric ANCOVA models.

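### The primary ANCOVA is valid and its 90% power holds, but it leaves out the Visit 1 oral ulcer count, a free pre-randomisation covariate whose value ranges from nothing to modest

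*SAP*

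**What the plan says.** The primary model in SAP 10.2.2 has "treatment, sex and region as factors; and the number of oral ulcers at baseline as a covariate". Protocol 10.6.1.2 names the same single disease covariate. SAP 5.3 fixes what it means: "baseline is defined as the last value measured on or before the day of the first dose of IP". SAP Table 2 assigns baseline to Visit 2.

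Visit 1 data exist. In Protocol Table 1 the row "Number of Oral Ulcers" is marked at Visit 1 as well as Visit 2, and so is the oral ulcer pain VAS. Inclusion criterion 5 (Protocol 7.2) opens with "Subjects must have at least 2 oral ulcers at Visit 1 (Screening Visit), and" and then sets a further minimum of 2 or 3 at Visit 2, depending on the gap between the visits.

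The AUC in SAP 4.2.5 runs over Visits 2 to 9. The imputation in SAP 10.2.2 covers Day 1 to Week 12. Neither these nor the listed sensitivity analyses name Visit 1, and no reason is given for leaving it out.

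On power, SAP 4.4 plans to "detect a treatment difference of 66 in the AUC of oral ulcer counts from Day 1 through Week 12" with 90% power "when the sample size in each group is 102, assuming a common standard deviation of 144".

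**The concern.** Protocol 4.2 prefers an AUC to a single post-baseline time point because oral ulcers flare and remit. The same reasoning applies before randomisation. One count, truncated by the entry rule, is a noisy measure of a subject's usual burden, and a second count up to 42 days earlier may carry information that the first does not. Adjusting for it leaves the estimand unchanged and introduces no bias, because it is measured before randomisation.

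What is at stake is precision on the primary test. The 13 ranked secondary endpoints in SAP Table 4 can be formally tested only if that test succeeds.

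**Working it through.** **Inputs.** Difference 66, SD 144, 102 per arm and two-sided 0.05 come from SAP 4.4. Visit days 1, 8, 15, 29, 43, 57, 71 and 85 come from Protocol Table 1. The trapezoidal rule comes from SAP 4.2.5. Correlation between visits and the effect of treatment on counts are assumptions.

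**1. The plan's own figure.** SE = 144 × √(2/102) = 20.16, and 66/20.16 = 3.27. The noncentral t distribution on 202 degrees of freedom gives power of 90.3%. The smallest n for 90% is 102 per arm. The stated 90% is reproduced with no covariate at all.

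**2. AUC weights.** The trapezoid gives 3.5, 7, 10.5, 14, 14, 14, 14, 7 (sum 84). The seven visits after Visit 2 have weights summing to 80.5 and squared weights summing to 992.25. The cross terms are 80.5² − 992.25 = 5488.

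**3. Algebra, ignoring the entry rule and treatment.** Take unit-variance counts with constant correlation r.
- Given Visit 2 only, residual variance = 992.25(1 − r²) + 5488(r − r²).
- Given Visits 1 and 2, replace r² by 2r²/(1 + r).
- At r = 0.3 these are 2055.4 and 1741.4. The ratio is 0.847, so the SE falls by 1 − √0.847 = 8.0%.
- At r = 0.2 the SE falls by 4.8%, and at r = 0.5 by 13.7%.
- With correlation half stable and half decaying (r from 0.2 to 0.7), the SE falls by 1.7% to 5.7%.
- With pure AR(1) decay it does not fall at all, because Visit 2 then holds everything that Visit 1 could tell.

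The direction is never harmful beyond the lost degree of freedom. The size depends entirely on the assumed structure.

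**4. Simulation with the entry rule and an active arm.** Counts were Poisson-lognormal, with an assumed 60% reduction on active.
- Persistent between-subject log-SD 0.5-0.9, transient log-SD 0.4-0.6, decorrelation time 20-40 days: residual AUC variance falls by about 3-13%.
- Mainly transient variation (persistent log-SD 0-0.3, transient 0.8): it falls by less than 1%.

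**5. Effect on power**, using SD × √(1 − v) for a fall v in residual variance. For the unadjusted reading, Visit 2 is assumed to explain 20% of the variance, so the starting SD is 144 × √0.8 = 128.8.

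| Fall in residual variance | 144 is the residual SD | 144 is the unadjusted SD |
|---|---|---|
| 0 | SD 144.0, power 90.3% | SD 128.8, power 95.4% |
| 1% | SD 143.3, power 90.6% | not computed |
| 3% | SD 141.8, power 91.1% | SD 126.9, power 95.9% |
| 13% | SD 134.3, power 93.7% | SD 120.1, power 97.4% |

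A fall of 3% to 13% is worth 102/0.97 − 102 ≈ 3 to 102/0.87 − 102 ≈ 15 extra subjects per arm.

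**6. Cost if Visit 1 adds nothing.** With 204 subjects and five model terms (intercept, treatment, sex, region, baseline), residual degrees of freedom are 199. Losing one inflates the SE by √(199/198) − 1 ≈ 0.25%.

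**The case against.** The strongest reply is that nothing is wrong. An ANCOVA on one pre-specified baseline is unbiased, and the stated power needs no covariate. This stands in full. A reader might infer that the plan is underpowered or its estimate flawed, but the documents show neither.

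The second reply is that the gain is assumed. This also stands. A reader might take the upper end of a simulation as the expected benefit. Placebo-only runs of the step 4 model reach a 17% fall, but that setting implies an AUC SD of about 270 or more, which does not fit the planned 144. Ignoring the treated arm also inflates the gain: in Phase 2, 70.9% of apremilast subjects were ulcer-free at Day 85 (Protocol 1.3), so Visit 1 has less left to predict there. Models with perfectly stable subject rates give more still: one placebo-only run had an AUC SD of 149 and an SE reduction of 11.1%. They leave out both the flares that Protocol 4.2 describes and the treated arm.

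Third, Visit 1 is not a clean replicate of Visit 2. The gap can be as short as one day, both counts are truncated by the entry rule, and corticosteroids or colchicine may still be in use at Visit 1 (Protocol 7.3 and 9.1). These features may dilute the gain, and the simulation does not model washout.

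Fourth, a reader might extend the point to the oral pain VAS at rank 2 or claim more precise imputation. Neither gain was computed. The VAS recalls the previous week, so readings less than seven days apart overlap.

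**Conclusion.** This is a free improvement, optional rather than a correction. The primary ANCOVA is valid and its 90% power holds. The Visit 1 ulcer count is available for every eligible subject and goes unused.

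The likely benefit is a fall in residual AUC variance of about 0-1% if variation is mainly transient and about 3-13% if subjects differ persistently. Both ranges rest on the Poisson-lognormal model and the assumed 60% reduction on active. Within them, power rises from 90.3% to at most about 94% if 144 is a residual SD. SAP 4.4 describes a t-test with a common SD, which reads more naturally as unadjusted. On that reading the Visit 2 covariate already takes power above 90%, and Visit 1 adds less. The range includes essentially no gain, so no single figure should be quoted as the precision lost.

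**What to change.** Before the Week 12 database lock, by which SAP Section 2 requires the SAP to be signed:

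- In SAP 10.2.2, add the Visit 1 oral ulcer count as a second covariate in the AUC ANCOVA.
- Include it as a variable in both imputation steps, the MCMC step and the monotone predictive mean matching step.
- Keep Visit 2 as baseline for the AUC and for all change scores.
- Record the change in SAP Section 14, which now declares no change to the protocol's statistical section, because Protocol 10.6.1.2 names the covariate.

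If the sponsor prefers not to alter the protocol-named model, a pre-specified supportive analysis with the Visit 1 count is a reasonable minimum.

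Adding the Visit 1 oral pain VAS to the rank 2 analysis is a separate option. It needs a rule for missing Visit 1 values, because the entry criteria guarantee the ulcer count but not the VAS.

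The cost is one degree of freedom (about 0.25% on the SE in the worst case), revised SAP text and a documented departure from the protocol. No new data are needed.

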### 1.3. Efficacy and Safety of Apremilast in Behçet's Disease

Apremilast has been studied for the treatment of BD in one completed Phase 2 study.

Study CC-10004-BCT-001 was a Phase 2, multicenter, randomized, placebo-controlled, double-blind, parallel-group study that assessed the safety and efficacy of apremilast in the treatment of Behçet's disease. The study consisted of 4 phases: a 12-week Screening Phase; a 12-week, Placebo-controlled Treatment Phase; a 12-week Dose Blinded Extension Phase; and a 4-week Posttreatment Observational Follow-up Phase.

A total of 111 subjects were randomized and treated with placebo or apremilast 30 mg twice daily (BID) (APR 30 BID) for 84 days. A total of 100 subjects completed the Double-blind Phase and opted to continue to the 12-week period of active treatment with APR 30 BID.

In the BCT-001 study, apremilast demonstrated a treatment benefit in subjects with BD with the achievement of the primary endpoint as subjects randomized to the APR 30 BID group had statistically significantly fewer oral ulcers on Day 85 compared with the placebo group. The mean oral ulcer counts at baseline were 2.7 and 2.9 in the APR 30 BID and placebo groups, respectively. On Day 85, the least squares (LS) mean oral ulcer counts were 0.4 and 2.0 in the APR 30 BID and placebo groups, respectively, yielding an LS mean difference (2-sided 95% confidence interval [CI]) of -1.6 (-2.4, -0.9) ( $p < 0.0001$ ).

The analyses of the secondary endpoints supported the results of the primary analysis. A significantly greater proportion of subjects in the APR 30 BID group achieved complete (oral ulcer-free) response at Day 85 compared with the placebo group (70.9% APR 30 BID; 28.6% placebo;  $p < 0.0001$ ). Similarly, a significantly greater proportion of subjects in the APR 30 BID group achieved partial ( $\geq 50\%$  reduction in oral ulcer number [including oral ulcer-free]) response at Day 85 compared with the placebo group (89.1% APR 30 BID group; 50.0% placebo group;  $p < 0.0001$ ). The area under the curve at Day 85 ( $AUC_{85}$ ) for oral ulcer count, average daily  $AUC_{85}$ , and average number of ulcers from Day 1 to Day 85 were more than 2-fold lower in the APR 30 BID group compared with the placebo group.

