### **10.3. Sample Size and Power Considerations**

The sample size estimation is based on the consideration from the results of the Phase 2 study CC-10004-BCT-001. A two-sided t-test at a 0.05 significance level will have 90% power to detect a treatment difference of 66 in the AUC of oral ulcer counts from Day 1 through Week 12 (AUC of placebo – drug = 66), the primary efficacy endpoint, when the sample size in each group is 102, assuming a common standard deviation of 144.

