4. INVESTIGATIONAL PLAN

4.1. Overall Study Design and Plan

This is a Phase 3, multicenter, randomized, double-blind, placebo-controlled, parallel group study, followed by an active-treatment extension phase to evaluate the efficacy and safety of apremilast (CC-10004) in the treatment of subjects with active Behçet's disease (BD).

Approximately 204 eligible subjects will be randomized 1:1 (102 subjects per group) to receive apremilast 30 mg BID (APR 30 BID), or identically-appearing placebo tablets BID for the 12-week Placebo-controlled Treatment Phase.

Upon completion of the Week 12 visit, subjects initially randomized to placebo will transition to APR 30 BID, while subjects initially randomized to APR 30 BID will continue on the same treatment during the 52-week Active Treatment Phase.

Subjects from German sites who complete Visit 14 of the 52-week Active Treatment Phase will have an opportunity to continue to receive APR 30 BID in an optional Open-label Extension Phase. Subjects who choose not to enter the optional Open-label Extension Phase will complete the 4-week Posttreatment Observational Follow-up Phase.

Subjects who discontinue at any time from the study for any reason are to enter the 4-week Posttreatment Observational Follow-up Phase.

The study will include the following:

- Screening Phase: up to 6 weeks
- Double-blind, Placebo-controlled Treatment Phase: 12 weeks
 - APR 30 BID
 - Placebo
- Active Treatment Phase: 52 weeks
 - APR 30 BID
- Optional Open-label Extension Phase for German Sites until apremilast is commercially available for BD or until the benefit/risk of apremilast is found not to be acceptable for BD, according to either the sponsor or health authority.
 - APR 30 BID
- Posttreatment Observational Follow-up Phase: – 4 weeks after the last dose (if a subject early terminates or, for subjects from German sites, choose not to enter the optional Open-label Extension Phase). Subjects from German sites who complete the optional Open-label Extension Phase do not need to complete the Observational Follow-up Visit.

Screening Phase

Screening procedures must be performed no more than 6 weeks prior to the start of study investigational product (IP) at Visit 2 (Day 1).

Treatment Phase

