The number of oral ulcers following subject's first loss of a complete response will be summarized for subjects who have a complete response prior to Week 12. The number of oral ulcers will be summarized as zero for subjects who had no reappearance of oral ulcers following a complete response prior to Week 12. The comparison between two treatment groups will be performed using ANCOVA model with the treatment, sex and region as factors and baseline number of oral ulcers as a covariate. Within-group LS means, the associated SEs, and treatment differences in LS means, the associated SE, and associated 2-sided 95% CIs and 2-sided p-values will be derived from the model. The treatment comparison will only be conducted if appropriate.

The summary tables with descriptive statistics for number of oral ulcers and general ulcers will be presented by treatment group at all applicable analysis visits.

Summary tables for change from baseline with descriptive statistics will be presented for continuous variables including pain VAS of oral ulcers, pain VAS of genital ulcers, BD Current Activity Form Scores, BD QoL scores, BSAS scores,

, and total score of the Static PGA of skin lesions by treatment group at all applicable visits per study period. For the PGA, only subjects who had BD skin lesions at baseline will be included. For the pain VAS of genital ulcers, only subjects who had genital ulcers at baseline will be included.

The LOCF approach will be used to impute the missing assessment at Week 12 for the following endpoints: pain VAS of oral ulcers, pain VAS of genital ulcers, BD Current Activity Form Scores, BD QoL, and BSAS. The change from baseline at Week 12 (LOCF approach) will be compared between the placebo and the APR 30 BID group using ANCOVA model with change from baseline at Week 12 as the response variable, treatment, sex and region as factors and baseline value as a covariate. Within-group LS means, the associated SEs, and treatment differences in LS means, the associated SE, and associated 2-sided 95% CIs and 2-sided p-values will be derived from the model. A sensitivity analysis for change from baseline in the pain VAS of oral ulcers at Week 12 will be conducted using mixed-effects model for repeated measures (MMRM) with treatment, visit, treatment-by-visit interaction, sex and region as factors and baseline value as a covariate. An unstructured covariance matrix that is homogeneous across treatment groups is to be used.

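### The ANCOVAs assume one residual variance without saying so; the Phase 2 ulcer counts make this doubtful, which affects arm-level SEs and unequal-sized subsets but not the primary comparison (minor)

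*SAP*

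**What the plan says.** SAP 10.2.2 compares AUC85 with a two-tailed parametric ANCOVA (treatment, sex and region as factors, baseline oral ulcer count as covariate). It draws "Within-group least-squares (LS) means, the associated standard errors (SE), and treatment differences in LS means", with the CI and p-value, from that one model, fitted in each imputed data set and combined in PROC MIANALYZE using the ANCOVA's own degrees of freedom.

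SAP 10.2.3 uses the same form for the change-from-baseline endpoints and for the number of oral ulcers after loss of response (rank 12, restricted to subjects with a complete response before Week 12). Rank 13 (skin PGA, subjects with lesions at baseline) is missing from the ANCOVA list in 10.2.3, but Protocol 10.6.1.3 gives continuous Week 12 endpoints a similar model. Rank 14 (genital ulcer pain) is limited to subjects with genital ulcers at baseline. SAP 10.4 fits the primary model within subgroups for the forest plot.

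None of these sections names an unequal-variance or robust option. The sample size in SAP 4.4 also takes one SD, "when the sample size in each group is 102, assuming a common standard deviation of 144". The one explicit statement is for the MMRM, a sensitivity analysis of oral ulcer pain only: "An unstructured covariance matrix that is homogeneous across treatment groups is to be used".

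**The concern.** Ulcer counts cannot fall below zero. A treatment that moves most subjects to zero lowers the spread as well as the mean, so equal residual variance is doubtful whenever the drug works.

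With equal arms, pooling leaves the SE of the treatment difference correct but gives both arms the same SE. With unequal arms the SE of the difference itself is biased, in a direction set by which arm is smaller. At stake are the arm-level SEs that the SAP plans to report, and the intervals and tests in subsets whose arm sizes randomisation does not hold equal. Ranks 12 to 14 are among these and belong to the formal testing sequence.

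**Working it through.** **1. The plan's own figure.** "A 2-sided t-test at a 0.05 significance level will have 90% power to detect a treatment difference of 66" (SAP 4.4), with 102 per group and SD 144. SE of the difference = 144 × √(2/102) = 20.16. The noncentral t distribution with 202 df gives power 0.903, so the stated 90% is reproduced.

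**2. Phase 2 inputs (Protocol 1.3).** 111 subjects; LS mean Day 85 counts 0.4 (apremilast) and 2.0 (placebo); ulcer-free 70.9% and 28.6%; the comparison is reported as "yielding an LS mean difference (2-sided 95% confidence interval [CI]) of -1.6 (-2.4, -0.9". Of the splits with 50 to 61 apremilast subjects, only 55 v 56 gives all four stated complete and partial response percentages. That means 39/55 and 16/56 ulcer-free.

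**3. Pooled SD.** CI width 1.5, t(109) = 1.982, so SE = 0.75/1.982 = 0.378. Pooled SD = 0.378/√(1/55 + 1/56) = 1.99 (1.86 to 2.13 for widths 1.4 to 1.6, allowing for rounding).

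**4. Apremilast SD.** With 39 zeros and 16 counts of at least 1, a mean of 0.40 is a total of 22. The SD then lies between 0.68 and 1.01, the maximum placing all surplus ulcers in one subject. A total of 24 (mean 0.44) allows at most 1.26.

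**5. Placebo SD.** s_P = √[(109 × pooled² − 54 × s_A²)/55].
- Pooled 1.99, s_A = 1.01: s_P = 2.62, ratio 2.6.
- Pooled 1.99, s_A = 0.68: s_P = 2.72, ratio 4.0.
- Pooled 1.86, s_A = 1.26 (least favourable rounding): s_P = 2.30, ratio 1.8.

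**6. Worst case for missing data.** Suppose missing subjects were counted as non-responders and 51 apremilast subjects were assessed (Protocol 1.3 has 7.3% of 55, that is 4, withdrawn from treatment for adverse events). Take 39 zeros, eleven counts of 1 and one of 11: total 22, mean 0.43, SD 1.57. Repeating steps 3 and 5 with 49 to 56 placebo subjects gives ratios of about 1.2 to 1.6. Each further missing apremilast subject lowers this floor.

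**7. Arm-level SEs at 102 v 102.** For SD ratio r (placebo/apremilast), pooled/true is √[(1 + r²)/2] for apremilast and that value divided by r for placebo.

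| r | apremilast | placebo |
|---|---|---|
| 1.4 | 1.22 | 0.87 |
| 2.0 | 1.58 | 0.79 |
| 2.9 | 2.17 | 0.75 |

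In AUC85 units, with the average variance held at 144² and r = 2, both arms would be given 144/√102 = 14.26, against true SEs of 9.02 and 18.04.

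**8. Treatment difference at 102 v 102.** True SE² = (s_A² + s_P²)/102, which equals the pooled form, so the SE is 20.16 either way. Simulated t-tests at r = 2 gave type I error 0.051 pooled and 0.051 Welch, and power 0.90 for both.

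**9. Unequal arms (illustrative splits, apremilast v placebo).** Pooled SE/true SE = √{[((n_A − 1) + (n_P − 1)r²)/(n_A + n_P − 2)] × (1/n_A + 1/n_P) / (1/n_A + r²/n_P)}.

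| Split | r = 1.4 | r = 2.0 | r = 2.5 | Type I error at r = 2: pooled, HC3 |
|---|---|---|---|---|
| 20 v 10 | 0.89 | 0.81 | 0.77 | 0.096, 0.046 |
| 85 v 55 | 0.93 | 0.88 | 0.85 | 0.089, 0.052 |
| 10 v 6 | 0.92 | 0.85 | 0.82 | 0.086, 0.043 |
| 10 v 20 | 1.12 | 1.23 | 1.29 | not tabulated (pooled SE too large) |

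The error rates come from simulated ANCOVAs and are approximate. The 10 v 6 split is the number of Phase 2 subjects with genital ulcers at baseline; the other splits are assumptions.

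**The case against.** Most of the opposing case stands.

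- **The primary test is sound.** A reader might infer that the primary analysis is invalid. Step 8 shows that it is not. Ranks 2, 3, 4 and 8 use the same near-1:1 ITT arms and are likewise essentially unaffected.
- **The ratio is inferred.** It is tempting to say that the protocol shows placebo to be two to three times as variable. Protocol 1.3 gives no SD or SE by arm. The figure treats LS means as raw means, the CI as a pooled t interval and response rates as observed zeros. Step 6 shows how far missing data could weaken it.
- **It covers one endpoint.** A reader might extend the ratio to every ANCOVA. Nothing in the documents gives one for AUC85, pain, BSAS, BDCAF, BD QoL or PGA. AUC85 also averages over eight visits and starts from similar baseline counts (2.7 and 2.9), which could make its ratio milder. Among rank 12 responders it is unknown.
- **The MMRM wording is not an error.** It serves one sensitivity analysis in near-equal arms, and the documents give no ratio for that endpoint. With seven post-baseline visits, arm-specific unstructured matrices need 56 covariance parameters instead of 28.
- **The affected comparisons are peripheral.** Ranks 12 to 14 are formally tested only if all earlier ranks succeed, and rank 12 is compared only if appropriate. The subgroup analyses assess consistency. SAP 5.1 and 10.1 require SDs by arm, so unequal spread would be visible.
- **Within-arm intervals are not clearly planned.** The CIs in SAP 10.2.2 read as those of the difference, so the arm-level problem is one of reported SEs.

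What remains is that those SEs are planned outputs, the unequal subsets are planned comparisons, and no planned analysis relaxes the equal-variance assumption. The AUC85 sensitivity analyses in 10.2.2 vary only the handling of missing data.

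**Conclusion.** The point holds as a minor one about reporting and subset inference. If SDs differ between arms by a factor of 1.4 to 2.9, the apremilast arm-level SE is about 1.2 to 2.2 times too large and the placebo SE about 0.75 to 0.87 of true. In the illustrative unequal splits with placebo smaller, at ratios of 1.4 to 2.5, the SE of the difference is about 0.77 to 0.93 of true. With placebo the larger arm, the error reverses and the interval is too wide.

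This rests on three assumptions: that the Day 85 back-calculation is broadly right, that some such heterogeneity carries over to the endpoints concerned, and that arm sizes in the subsets turn out unequal. The documents make the first likely and leave the other two open. They do not support a claim against the primary analysis or against the MMRM specification.

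**What to change.** In SAP 10.2.2, 10.2.3 and 10.4, state the variance assumption and compute HC3 standard errors for the LS means and their differences. Alternatively, fit a treatment-specific residual variance with Satterthwaite or Kenward-Roger degrees of freedom (for example PROC MIXED, REPEATED / GROUP=treatment). For AUC85, do this in each imputed data set before PROC MIANALYZE; for the LOCF endpoints, in the single analysis data set. If Satterthwaite or Kenward-Roger degrees of freedom are used, rewrite the complete-data degrees-of-freedom sentence in 10.2.2, because they can differ between imputations.

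The cost is SAP wording and a small change in code, with no new data and no material change at 102 v 102. In very small subsets such as 10 v 6, intervals will be slightly wider and, with arm-specific variances, degrees of freedom fewer, since one variance would rest on about six subjects. Leave the MMRM covariance as specified; a treatment-specific matrix there is optional.
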